2.7.1 Secondary endpoints

Following are the secondary endpoints to be considered for analysis by 12 months post LPFT and for complete available data for the study. Additionally for OS analysis by 24 months post LPFT will also be analyzed.

A listing of all responses assessments by subject will be provided including BOR, PFS time, PFS event (yes/no), OS time, death date and duration of CR. Bone marrow blasts percentage will also be listed. In addition, for some selected laboratory parameters and for bone marrow blasts percentage, trends over time will be displayed via boxplots and corresponding tables displaying the summary statistics for these selected timepoints to be produced.

2.7.1.1 Complete remission rate:

Complete remission rate will be assessed according to International Working Group (IWG) for MDS (2006) with MBG453 (sabatolimab) in combination with HMAs (IV/SC/Oral) in subject with intermediate, high, or very high risk MDS.

Proportion of subjects achieving CR will be presented together with an exact 95% confidence interval.

A sensitivity analysis may be performed for CR by considering IWG-MDS & modified IWG-MDS of Peripheral blood.

If any subject who achieved CR and discontinued/lost to follow-up within 12 months will be considered as Responder.

If any subject who achieved CR and undergone to Bone Marrow Transplantation (BMT) within 12 months will be considered as Responder.

Subjects who discontinue early before achieving response will be considered as non-responders. Similarly subjects with transplant or subjects with progression before achieving response will be considered as non-responders. As appropriate, additional sensitivity analyses will be performed excluding discontinued subjects, transplant subjects and subjects with progression before documentation of CR.

Response assessment rules

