Response assessment will be performed by the investigator according to the assessment schedule depicted in protocol Table 8-1 based on available bone marrow assessment and peripheral blood every 3 cycles for core phase during the first 07 cycles and every 6 cycles for extension phase and all transfusions records as detailed in [Table 2-6](#) using the modified version of the published response criteria IWG for MDS. Moreover, response assessments can be performed at any time if clinically indicated, e.g. for confirmation of response but also for any suspicion of progression/relapse. These assessments are recorded as an unscheduled visit in the eCRFs and will be considered for the overall determination of response and progression/relapse with the respective assessment date.

The investigator does not determine best overall response, he/she is assessing only the response based on the given bone marrow and peripheral blood data, the history of transfusions and myeloid growth factor received within the last 2 weeks.

The best overall response (BOR) will be derived based on the CR secondary endpoint rules by Novartis as below:

- CR = at least one determination of CR without progression or relapse from CR within the four after CR.
- mCR = at least one determination of mCR (and not qualifying for a CR).
- PR = at least one determination of PR (and not qualifying for a CR/mCR).
- SD = at least one SD assessment and not qualifying for CR, mCR or PR.
- PD = progression after enrollment and not qualifying for CR, mCR, PR or SD.
- UNK = all other cases (i.e., not qualifying for confirmed CR or mCR or PR and without SD or progression).

Details on the definition of response categories which are to be captured in the eCRF by the investigator were defined in Table 8-2 of the protocol that was copied into Table 2-6 below.

Table 2-6 Modified response classification per IWG criteria in MDS

| Response category | Definition [#] |
|-------------------|-------------------------|
|-------------------|-------------------------|

| | |
|--|--|

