2.7.1.6 Duration of Complete Remission

Duration of Complete Remission (DOR) is the time from the date of the first documented CR to the date of first documented relapse from CR or death due to any cause, whichever occurs first.

The start date is the date of first documented CR and the end date is defined as the date of the first documented relapse from CR or death due to any cause. Duration of CR for Subjects without event will be censored at the date of their last adequate response assessment.

DOR will be analyzed using the Kaplan-Meier method. Estimates of the 25th, median and 75th percentile of the DOR and their 95% confidence intervals will be provided, Kaplan-Meier curves will be produced, if applicable.

- DOR applies only to subjects who have CR (responded).

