2.7.1.7 Time to Complete Remission

Time to Complete Remission is defined as the time from the date of enrollment (cycle 1 day 1) to the first documented CR.

Time to complete remission will be analyzed using the Kaplan-Meier Product-Limit method. Subjects who are known to be without CR will be censored at study-maximum follow-up time (i.e. Last Subject Last Visit (LPLV) for final analysis, for analysis of cut-off date min (LPLV, Cut-off date)) for subjects with a PFS event (i.e. disease progression or death due to any cause), or at the date of the last adequate assessment for subjects without a PFS event. Estimates of the 25th, median and 75th percentile of the time to CR and their 95% confidence intervals Kaplan-Meier plots will be provided, if applicable. Improvement in RBC/platelets transfusion independence

The number and percent of subjects who are RBC/platelets transfusion independent after the date of enrollment as per IWG-MDS will be provided.

RBC/Platelets transfusion independence rate is defined as the proportion of subjects having received <0 units (no RBC/Platelets transfusions) during at least 8 consecutive weeks after enrollment ([Table 2-6](#)). The number and percentage of subjects will be shown for the overall FAS and then also in only those with transfusion dependence at baseline. Percentages will be provided with exact 95% Clopper-Pearson confidence intervals. Bar graphs will be provided.

For subjects with at least one period of transfusion independence post-baseline, the total duration of all transfusion independence periods (which all individually must be at least 8 weeks) will be also summarized.

The duration of each period of transfusion independence is defined from the end date of the last transfusion received until the date transfusions are given again or last date of treatment administration in case transfusions had not (re-)started during treatment. The total duration of all transfusion independence periods is the sum of each period of the transfusion independence.

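### The SAP defines complete remission in two ways, one with a time window that has no unit, so CR counts may differ between tables and a relapsed CR can be reported as unknown

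*SAP*

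**What the plan says.** For the CR rate, SAP 2.7.1.1 states: "Proportion of subjects achieving CR will be presented together with an exact 95% confidence interval". Protocol 12.5.1.1 has the same proportion, by 12 months. Neither asks that the remission last. The same SAP section also counts as a responder anyone who reached CR and then discontinued, was lost to follow-up or went to transplant within 12 months. SAP 2.7.3 limits which assessments count towards CR (after enrollment, before other anti-neoplastic therapy or HSCT), again with no durability requirement.

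SAP 2.7.1.1 then sets out a BOR hierarchy, introduced by "The best overall response (BOR) will be derived based on the CR secondary endpoint rules by Novartis as below". The rows that matter are:

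- The top row, which carries the durability condition: "CR = at least one determination of CR without progression or relapse from CR within the four after CR"
- The row for stable disease, which depends on an assessment recorded as such: "SD = at least one SD assessment and not qualifying for CR, mCR or PR"
- The row for progressive disease, which does not mention relapse: "PD = progression after enrollment and not qualifying for CR, mCR, PR or SD"
- The residual row, which catches whatever is left over: "UNK = all other cases (i.e., not qualifying for confirmed CR or mCR or PR and without SD or progression"

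The mCR and PR rows each need a determination of that category. SAP 2.7.1.5 builds the response rate on BOR.

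For duration of CR, SAP 2.7.1.6 says "The start date is the date of first documented CR" and restricts the analysis to subjects who have CR and responded. SAP 2.7.1.7 says "Time to Complete Remission is defined as the time from the date of enrollment (cycle 1 day 1) to the first documented CR".

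**The concern.** There are three linked problems.

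1. **The window has no unit.** Weeks, cycles and months all fit the sentence, and nothing elsewhere in either document supplies the unit. The BOR flag cannot be programmed without a guess. The residual row also relies on a confirmed CR, and no confirmation rule exists.
2. **The hierarchy has a gap.** Relapse from CR is its own category in SAP Table 2-6, but the PD row mentions only progression. A participant with a documented CR and a documented relapse can end up as unknown, which misdescribes a known outcome.
3. **Related outputs use different sets of CRs.** A remission that fails the window is not a CR in BOR or in the response rate. It is still a CR in the CR rate and an event in time to CR, and it has a start date for duration of CR.

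With 39 enrolled, the first-listed secondary endpoint rests on few cases, so a single difference in count shows.

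**Working it through.** **The plan's own figures.** The plan gives no number for this point. Its only design figure is the precision-based sample size, which reproduces and is not in dispute: 1.96² × 0.30 × 0.70 / 0.10² = 80.67, so 81.

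**Which relapses are not progression.** In SAP Table 2-6 the neutrophil, platelet and transfusion-dependence criteria are the same for relapse and for progression. Two relapse criteria go further: return to the baseline marrow blast percentage, and a hemoglobin fall of at least 1.5 g/dL to below 10, where progression needs at least 2 g/dL. A return to baseline blasts, or a fall of 1.5 to under 2 g/dL to below 10, is therefore relapse alone.

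**Running the hierarchy.** BOR was derived for short histories under three readings of the window (28 days, 112 days, about 122 days):

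| History | 4 weeks | 4 cycles | 4 months |
|---|---|---|---|
| CR day 85, relapse alone day 106 | unknown | unknown | unknown |
| CR day 85, relapse alone day 169 (next scheduled assessment) | CR | unknown | unknown |
| CR day 85, progression day 106 | PD | PD | PD |
| SD day 85, CR day 169, relapse alone day 190 | SD | SD | SD |
| mCR day 85, CR day 169, relapse alone day 190 | mCR | mCR | mCR |

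Every history contains a documented CR, so each counts as an event in time to CR and has a start date for duration of CR.

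**Value of one participant.** With the FAS taken as 39 (enrolled number, SAP 1.1), 1/39 = 2.6 points. As an illustration, 8/39 = 20.5% (exact 95% CI 9.3 to 36.5) against 7/39 = 17.9% (7.5 to 33.5).

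**How many participants could be affected.** Inputs, all used as assumptions:

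- 4 to 13 first CRs (4/39 = 10.3%, 13/39 = 33.3%). This spans the 9% decitabine CR rate in protocol 1.1 (0.09 × 39 = 3.5) to the 33.3% reported for sabatolimab plus decitabine in protocol 4.3.2.
- Exponential CR duration with median m = 10.3 months (decitabine responses, protocol 4.3.1) or m = 18 months (the upper bound for HMA responses in protocol 4.1).

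The chance of losing a CR within W months is q = 1 − 0.5^(W/m). With x CRs, the expected number affected is x·q, and the chance of at least one is 1 − (1 − q)^x. One month is 30.4375 days (SAP 2.1.1.5).

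| Window | W (months) | m | q | Expected, x = 4 to 13 | At least one |
|---|---|---|---|---|---|
| 4 weeks | 0.92 | 10.3 | 6.0% | 0.24 to 0.78 | 22% to 55% |
| 4 weeks | 0.92 | 18 | 3.5% | 0.14 to 0.45 | 13% to 37% |
| 4 cycles | 3.68 | 10.3 | 21.9% | 0.88 to 2.85 | 63% to 96% |
| 4 cycles | 3.68 | 18 | 13.2% | 0.53 to 1.72 | 43% to 84% |
| 4 months | 4.00 | 10.3 | 23.6% | 0.94 to 3.07 | 66% to 97% |
| 4 months | 4.00 | 18 | 14.3% | 0.57 to 1.86 | 46% to 86% |

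These are participants who fail the window for any reason. Those classed as unknown are a subset.

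**The case against.** The strongest reply is that the main outputs already agree. The CR rate, time to CR and the start of duration can all be read as any documented CR, which matches protocol 12.5.1.1, 12.5.1.6 and 12.5.1.7. On that reading the window touches only BOR, the response rate and a listing. This stands, and it rules out an inference a reader might draw: that the CR rate itself moves with the unit. With 8 CRs and a 10.3-month median, 8 × (1 − q)/39 would give 19.3%, 16.0% or 15.7% for weeks, cycles or months, but only if the CR rate means BOR = CR. The SAP never says that. Its introductory sentence derives BOR from the CR endpoint rules, not the reverse. Because the list sits inside the CR-rate section, though, the other reading remains open, and it would conflict with the responder rule.

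Other parts of the reply also hold:

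- Most relapses meet a progression criterion too and can land in PD. Unknown also requires that no mCR, PR or SD was ever recorded. It would be wrong to say that every CR failing the window becomes unknown.
- Scheduled core-phase response assessments are 84 days apart, so a four-week window contains none after the CR visit. Only interim counts (protocol 8.3 has hematology on days 1 and 8 of each cycle) or an unscheduled assessment could trigger it. The exponential model ignores this and may overstate the four-week figures.
- The 10.3-month median concerns all responses in that trial, not CRs.
- Duration of CR is limited to subjects who responded, so whether an early relapser belongs there is ambiguous rather than settled.
- BOR and duration of CR are listed by subject, so a mismatch would be visible. The listing would not say which count is intended.

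The SAP shows no redaction at the gap, but a word lost in file conversion cannot be excluded. Restoring a unit would settle only the first problem.

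**Conclusion.** The point holds as an unreconciled definition. The SAP uses any documented CR for some outputs and a windowed CR for BOR and the response rate. The window has no unit, and relapse-only failures can be reported as unknown. That last result follows from the rules as written and is not just missing detail.

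A reader might infer that the tables cannot reconcile. The documents do not support that: a mismatch needs at least one relapse or progression inside the window, and if the unit is weeks there may well be none. Under the stated assumptions (FAS of 39, 4 to 13 CRs, exponential duration, median 10.3 or 18 months) the expected number is below one for weeks and about 0.5 to 3 for cycles or months, at 2.6 points each.

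The endpoint is secondary and descriptive with no hypothesis test, so no error rate or power is affected. This is a should-fix.

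**What to change.** 1. State that the CR rate, time to CR and duration of CR all use the protocol's definition, any documented CR. Do not carry the durability condition into time to CR or duration: it would depart from protocol 12.5.1.6 and 12.5.1.7, and it would remove the shortest remissions and push median duration up.
2. For BOR, either remove the durability condition, or write out its unit, label the category durable CR, and reconcile its count with the CR rate in a table footnote.
3. If the condition stays, class a CR that fails it as mCR when the mCR criteria were met, including the blast decrease of at least 50% that CR itself does not require. Otherwise use the next rule that applies. Treat relapse from CR as PD, never as unknown.
4. Define the word confirmed in the residual row, or delete it.

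The SAP's document history places its latest update after database lock, so the choice should be recorded in writing with its date and not left to programming. The cost is a few lines of SAP text and re-derivation of one flag.

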Safety profiles of decitabine and azacitidine are similar. Azacitidine and decitabine are generally well tolerated and both have a manageable toxicity profile (Derissen et al 2013). The most common toxicity is myelosuppression, primarily neutropenia and thrombocytopenia. Adverse events related to myelosuppression typically occur in the third week of the treatment cycle and participants commonly achieve hematologic recovery prior to the next treatment cycle. Otherwise, a delay in starting the next cycle or a dose reduction may be necessary. During the clinical trials, hematologic adverse events were most frequently observed during the first two treatment cycles and nadir values for hematological parameters improved during subsequent cycles. The most common non-hematological adverse events corresponded to gastrointestinal toxicities (nausea, vomiting, diarrhea, and constipation) which generally occurred in the first week of the treatment cycle. These events were generally mild and transient. They could be managed with concomitant medications, including antiemetics and antidiarrheal.

Azacitidine and decitabine regimens used in this trial are the most studied regimens and recommended by international treatment guidelines.

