| Disease progression | 
At least 1 of the following criteria is met:
 
[In absence of another explanation not due to MDS, such as acute infection, bleeding, hemolysis, etc. Note that observation of peripheral blasts is not a sufficient criterion for progression. However in that case, a bone marrow examination should be made to determine whether relapse has occurred.]
 
Bone marrow according to the number of blasts of the subject at baseline:
 
 1. Less than 5% blasts at baseline: $\geq 50\%$ increase in blasts over baseline to $>5\%$ blasts 2. 5%- $<10\%$ blasts at baseline: $\geq 50\%$ increase over baseline to $>10\%$ blasts 3. 10%- $<20\%$ blasts at baseline: $\geq 50\%$ increase over baseline to $>20\%$ blasts. Subjects with more than 20% of blasts will be considered to have transformation to acute leukemia per 2016 WHO classification (Arber et al 2016) 
Peripheral blood:
 
 1. Decrease of $\geq 50\%$ from maximum remission/response*** levels in neutrophils AND neutrophils $<1.0 \times 10^9/L$. Note: neutrophils counts during periods of active infection will not be considered in determining the maximum 2. Decrease of $\geq 50\%$ from maximum remission/response*** levels in platelets AND platelets $<100 \times 10^9/L$ 3. Reduction from maximum remission/response*** levels in Hgb by $\geq 2\text{g/dL}$ AND Hgb $<10\text{g/dL}$ 
Becoming transfusion dependent** Occurrence of acute leukemia or extramedullary leukemia per investigator's judgement
 |
|----------------------------|---|

| Modified Hematological Improvement per IWG-MDS criteria in MDS (Cheson et al 2006) | |
|---|---|
| HI category | Definition[#] (HI must last at least 8 weeks) |
| Erythroid response (HI-E) (pretreatment*, $<11\text{ g/dL}$) | 
 1. Hgb increase from baseline by $\geq 1.5\text{ g/dL}$, in at least 2 consecutive Hgb measurements and maintained over at least 8 weeks 2. Relevant reduction from baseline of units of RBC transfusions by an absolute number of at least 4 RBC transfusions/8 weeks compared with the pre-treatment transfusion number in the previous 8 weeks. Only RBC transfusions given for a Hgb of $<9\text{ g/dL}$ pre-treatment will count in the RBC transfusion response evaluation. |

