****Definition of transfusion dependence and independence for red blood cells (RBC) and/or platelets are described below.**

****maximum remission/response levels correspond to the best values reported in post baseline.*

Transfusions Status Definitions for RBC/platelets

Transfusions for intercurrent diseases not due to MDS (e.g. bleeding, surgical procedure, hemolysis, infections) should not be taken into account for the following:

Transfusion dependence:

1. At baseline: subjects having received ≥ 3 units of transfusion within the 8 consecutive weeks prior to baseline.
2. Post-baseline: subjects having received ≥ 3 units of transfusion within any 8 consecutive weeks during the course of the study.

Transfusion independence:

1. At baseline: subjects having received 0 units of transfusion within any 8 consecutive weeks prior to baseline.
2. Post-baseline: subjects having received 0 units of transfusion within any 8 consecutive weeks during the course of the study.

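### The transfusion criterion for progression has no baseline comparator, so investigator-assessed PFS can include transfusion-only events in participants whose need has not worsened

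*SAP*

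**What the plan says.** Progression in SAP Table 2-6 (copied from Protocol Table 8-2) is met when "At least 1 of the following criteria is met". The list covers marrow blasts, neutrophils, platelets, hemoglobin, leukemia and "Becoming transfusion dependent". The footnote to that last item points to the transfusion status definitions:

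- Dependence before treatment: "At baseline: subjects having received ≥ 3 units of transfusion within the 8 consecutive weeks prior to baseline".
- Dependence on study: "Post-baseline: subjects having received ≥ 3 units of transfusion within any 8 consecutive weeks during the course of the study".
- Independence before treatment: "At baseline: subjects having received 0 units of transfusion within any 8 consecutive weeks prior to baseline".

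Transfusions for intercurrent disease not due to MDS are left out, and every progression criterion requires that no other non-MDS explanation exists. The investigator makes the assessment (SAP 2.7.1.1). Under SAP 2.7.1.2, progression is a PFS event.

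**The concern.** The baseline state is judged on one fixed 8-week window. The on-study state is judged on the worst of many overlapping windows over a year or more. Nothing in the on-study definition requires an increase over baseline, an earlier transfusion-free period, or a minimum time on treatment.

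The rest of the plan does use comparators. The count criteria compare with the best post-baseline value. The erythroid improvement criterion compares RBC units with the pre-treatment 8 weeks. Protocol 6.1.4.1 compares transfusion need at progression with need before enrollment. Read literally, a participant falling from 8 to 4 RBC units per 8 weeks would meet erythroid improvement (a fall of at least 4) and on-study dependence (at least 3) in the same window.

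The listed exclusions do not name marrow suppression from the hypomethylating agent, although Protocol 4.3.1 reports that "hematologic adverse events were most frequently observed during the first two treatment cycles and nadir values for hematological parameters improved during subsequent cycles".

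The 12-month PFS rate is a named secondary objective. Events without worsening lower it and tie it to the transfusion mix at entry. Nothing planned would show this: SAP 2.7.1.2 summarizes censoring reasons but not events by criterion, and SAP section 4 drops supportive and sensitivity analyses.

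**Working it through.** The plan states no figure on this point, so there is none to reproduce.

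**Step 1: who is covered by the wording.**

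| Units in the 8 weeks before baseline | Status in Table 2-6 | Can the participant *become* dependent? |
|---|---|---|
| 3 or more | dependent | On a plain reading no, but no rule says so |
| 1–2 | neither dependent nor (on that window) independent | Yes, at 3 units in any later window |
| 0 | independent | Yes |

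**Step 2: a hand check for the middle row.** Inputs from the documents are the threshold of 3 units and the 8-week window. Assumptions are single-unit transfusions arriving at random (Poisson) with a constant mean λ per 8 weeks. For one window, P(N ≥ 3) = 1 − e^(−λ)(1 + λ + λ²/2).

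- λ = 2: 1 − e^(−2) × 5 = 0.323
- λ = 1: 1 − e^(−1) × 2.5 = 0.080

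Counting only non-overlapping windows (3 in 24 weeks, 6 in 48 weeks) gives a floor for the rolling definition:

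- λ = 2: 1 − 0.677³ = 0.69, and 1 − 0.677⁶ = 0.90
- λ = 1: 1 − 0.920³ = 0.22, and 1 − 0.920⁶ = 0.39

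**Step 3: the rolling window, by simulation.** The settings use 20,000 to 40,000 simulated participants each. Mean need is the same before and after baseline, the 8-week window moves daily, and results are restricted to participants with fewer than 3 units in the baseline window. Episodes are 1 or 2 units, and spacing is random (Poisson) or fairly regular (gamma, shape 4). Cells give the chance of at least one window with 3 or more units.

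| Steady need per 8 weeks | Episode and spacing | By week 24 | By week 52 |
|---|---|---|---|
| 2 units | single, random | 80% | 98% |
| 2 units | single, regular | 84% | 99% |
| 2 units | two-unit, random | 69% | 93% |
| 2 units | two-unit, regular | 75% | 96% |
| 1 unit | single, random | 33% | 62% |
| 1 unit | single, regular | 9% | 21% |
| 1 unit | two-unit, random | 32% | 60% |
| 1 unit | two-unit, regular | 15% | 33% |
| 0.5 unit | random, single or two-unit | 8–11% | 18–25% |

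Repeat runs move the ends by a point or two. I therefore quote about 70–86% by week 24 and 92–99% by week 52 at 2 units, and about 21–62% by week 52 at 1 unit.

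**Step 4: what these chances are.** They are chances that the count is crossed with no change in underlying need. They are not forecasts of recorded PFS events, because an investigator must judge each case and may find another explanation.

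**The case against.** The strongest reply is that the criterion turns on *becoming*. Baseline dependence is defined separately at the same threshold and window length, so a participant already dependent cannot become so. This is the better reading. A reader might infer that staying dependent is automatically a PFS event and multiply by an assumed dependence rate among the 39. The documents support neither step: the wording points the other way and no baseline rate is given. What remains is that the rule is unwritten, and that *becoming* does nothing for the 1–2 unit group.

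Second, investigators assess progression; no programmed scan of units is described, and the list of other explanations is open-ended. That stands. It means the simulated chances are not event rates, and it does not support a claim that events would be dated to the first months, since a recorded date depends on when an assessment is made. However, no exclusion removes ordinary MDS-related transfusions, and leaving the question to judgment without a rule invites inconsistency between sites.

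Third, a reader might infer that later remitters become CR non-responders, because "subjects with progression before achieving response will be considered as non-responders". But the best-overall-response rule in the same section looks only for progression or relapse after a CR, so an earlier progression does not cancel a later one. Those two clauses need reconciling with each other; they do not establish a loss of CRs here.

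Finally, the study has one arm, no hypothesis test and descriptive PFS, and the current SAP addendum postdates database lock. This argues against replacing the endpoint. It does not argue against showing how PFS events arose.

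**Conclusion.** The point holds in a limited form. The on-study definition lacks a baseline comparator, its application to participants dependent at baseline is unstated, and participants with 1–2 baseline units can meet it without worsening. For a steady 2 units per 8 weeks this is likely within the year; for 1 unit it is possible; for 0.5 unit it is uncommon. These statements rest on an assumed constant need, 1- or 2-unit episodes, random or fairly regular spacing, and no transfusion being excluded as non-MDS.

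The direction of the bias on the 12-month PFS rate is downward. Its size in this trial cannot be derived from the documents.

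**What to change.** Keep the investigator-assessed PFS as the reported analysis. In SAP 2.7.1.2:

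1. State that a participant dependent at baseline cannot meet the transfusion criterion through unchanged need.
2. Tabulate PFS events by criterion: blasts, counts, transfusion only, leukemia, death.
3. Add one supplementary PFS, labelled post hoc, that does not count transfusion-only events lacking an increase over the participant's own pre-enrollment 8-week need. State a margin for that increase: 3 units always exceeds 1 or 2, so without a margin the 1–2 unit group would be unaffected. The 4-unit change per 8 weeks already used for erythroid improvement is one candidate for red cells.
4. Describe follow-up after each discounted event, and record the addition in SAP section 4.

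The cost is modest. Transfusions are recorded from 16 weeks before enrollment (Protocol 6.2.1), and SAP 2.4.2 already separates the MDS-related ones. The documents do not show that the criterion behind each progression is captured, so step 2 may have to be derived from blasts, counts and transfusion records.

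The main weakness is follow-up. Protocol sections 3 and 8.3 let response assessments end at documented progression, while section 9.1.1 reads as continuing them to end of study. Where they stopped, censoring after a discounted event may be informative, and the supplementary estimate could then be too favorable.

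Any use of the same definition in treatment decisions is for the sponsor to reconcile.
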